# Statistical Analysis Plan

GlaxoSmithKline

Study alias & e-track number(s): ZOSTER-063 (204928)

**VAS** Visual Analogue Scale

**YOA** Years of Age

# Statistical Analysis Plan

GlaxoSmithKline

[figure not shown]
Study alias & e-track number(s): ZOSTER-063 (204928)

## 1. DOCUMENT HISTORY

Date	Description	Protocol Version
30-MAY-2017	Version 1	Amendment 2 - 16-NOV-2016

## 2. STUDY DESIGN

This study is a Phase III, open label, multi-center study with a single group.

DC = Diary Card.

† Visit 3 at Day 7 is defined as 7 days post dose 1 at Visit 2 (Month 0) and Visit 5 at Day 67 is defined as 7 days post dose 2 at Visit 4 (Month 2).

‡ Diary Cards distributed at Visit 2 and Visit 4 for solicited adverse events (Days 0–6) will be collected on Day 7 and Day 67 (Visit 3 and Visit 5), respectively.

§ Questionnaires distributed at Visit 2 and Visit 4 will be collected on Day 7 and Day 67 (Visit 3 and Visit 5), respectively.

\* The Month 3 contact will occur when the post-vaccination 2 (Days 0–29) diary cards have been received by site (returned by mail).

The following group names will be used for the statistical analyses:

Group order in tables	Group label in tables	Group definition for footnote
1	HZ/su	Herpes Zoster subunit vaccine

The following sub-groups will be used for the statistical analysis:

# Statistical Analysis Plan

GlaxoSmithKline

Study alias & e-track number(s): ZOSTER-063 (204928)

**Table 1 Details of subgroups**

Sub-group category	Sub-group order in tables	Sub-group label in tables	Sub-group definition for footnote
Age	1	50-59 YOA	50-59 year old subjects
	2	60-69 YOA	60-69 year old subjects
	3	≥ 70 YOA	≥ 70 year old subjects
Frailty Index (FI)	1	Non-Frail	Subjects with frailty index <=3 are considered as Non frail
	2	Pre-Frail	Subjects with frailty index >3 and <=8 are considered as pre fail
	3	Frail	Subjects with frailty index >8 are considered as frail
Maximum Intensity / Reactogenicity Grade	1	Grade 0	Subjects with no solicited symptoms reported.
	2	Grade 1,2	Subjects with at least one grade 1 or 2 (=mild or moderate) solicited AE reported as maximum intensity.
	3	Grade 3	Subjects with at least one grade 3 (=Severe) solicited AE reported as maximum intensity.
Type of Symptom*	1	None	Subjects with no solicited symptom reported
	2	Local	Subjects with at least one solicited local symptom reported
	3	General	Subjects with at least one solicited general symptom reported
Gender	1	Male	Male Subjects
	2	Female	Female Subjects

\*Note that a subject can be included in both Local or General categories

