1.2. Rationale for the study and study design

1.2.1. Rationale for the study

Nearly 22,900 subjects received the active HZ/su study vaccine in clinical trials worldwide, most of whom (95%) were ≥ 50 YOA. Due to the high efficacy of the vaccine, most HZ and PHN cases were prevented, thus avoiding any negative impact on QoL in those subjects. No imbalance between the vaccine and the placebo arms were found in terms of SAEs, potential Immune-Mediated Diseases (pIMDs) or death during the entire duration of the studies. The vaccine was generally well tolerated. However, the vaccine was more reactogenic than placebo (saline solution).

In the pooled analysis of the ZOSTER-006 and ZOSTER-022 studies the most common side effects were at the site of injection, including pain, redness, and swelling. Up to 70% of people who received the HZ/su vaccine had pain at the injection site. These symptoms were usually mild and resolved within about 3 days on average. The incidence of grade 3 solicited local pain, was about 4%, with an average duration of less than 2 days. Grade 3 reactogenicity is defined as preventing ADL. Other side effects seen in more than 10% of people who received the vaccine included myalgia, fatigue, headache, shivering, fever

and gastrointestinal symptoms such as nausea, vomiting, diarrhoea and/or abdominal pain. The incidence of myalgia and fatigue was about 33% (overall/dose) and had an average duration of 2.5 days. The incidence of grade 3 solicited general symptoms was 3% or less (overall/dose) with average durations of less than 2 days. The reactogenicity is likely to be secondary to the enhanced innate immune responses elicited at the site of injection and therefore is expected [Didierlaurent, 2014]. This is consistently observed in studies evaluating AS01 – (and other) adjuvanted vaccines, in which higher reactogenicity is observed with adjuvanted versus non-adjuvanted vaccines [Stassijns, 2016].

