While grade 3 reactogenicity is defined as preventing ADL, there is no clear understanding available on how this translates to impact on the daily Physical Functioning (PF) of an individual. As such this study is designed to quantify the impact of reactogenicity in terms of PF (e.g., walking, carrying groceries, climbing stairs, etc.). In addition, the Quality-adjusted life year (QALY) loss associated for both *Zostavax*-vaccinated and non-vaccinated subjects with a HZ case that did not lead to PHN, has been estimated to be approximately 0.01 (i.e., 3.65 days) [Pellissier, 2007]. For HZ cases that led to PHN, it was between 38.69 and 56.94 days, resulting in QALY losses of 0.106–0.156 depending on age for non-vaccinated subjects, [Pellissier, 2007]. Similar results were observed in the ZOSTER-006 and ZOSTER-022 studies with the HZ/su vaccine. As such, QALY loss can be avoided by preventing HZ and PHN, through HZ/su vaccination. However reductions in QALY loss by preventing HZ and PHN through HZ/su administration could be partially offset by the QALY loss related to reactogenicity that is associated with vaccination.

In assessing the impact on QoL, the QALY loss due to adverse events is an important parameter to include when calculating the cost/effectiveness of HZ/su compared to no vaccination. These data will be included in models which analyze net QALY loss avoided by preventing HZ and PHN by vaccinating with HZ/su. Furthermore, only limited data are available to assess the impact of the reactogenicity on the Quality of Life (QoL) and PF of individuals exposed to the HZ/su vaccine or vaccination in general. These data are important to both Health Care Providers (HCPs) and policy makers. Additional characterization of the reactogenicity will allow vaccinators to better inform vaccinees before the administration of the vaccine. Therefore, this study will be conducted to enhance our understanding of HZ/su vaccine reactogenicity, and to provide more complete information to vaccinators and persons who will receive the vaccine.

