8.3.3.2. Assessment of adverse events**8.3.3.2.1. Assessment of intensity**

The intensity of the following solicited AEs will be assessed as described in [Table 13](#).

Table 13 Intensity scales for solicited symptoms in adults

Adverse Event	Intensity grade	Parameter
Pain at injection site	0	None
	1	Mild: Any pain neither interfering with nor preventing normal every day activities.
	2	Moderate: Painful when limb is moved and interferes with every day activities.
	3	Severe: Significant pain at rest. Prevents normal every day activities.
Redness at injection site		Record greatest surface diameter in mm
Swelling at injection site		Record greatest surface diameter in mm
Fever*		Record temperature in °C/F
Headache	0	Normal
	1	Mild: Headache that is easily tolerated
	2	Moderate: Headache that interferes with normal activity
	3	Severe: Headache that prevents normal activity
Fatigue	0	Normal
	1	Mild: Fatigue that is easily tolerated
	2	Moderate: Fatigue that interferes with normal activity
	3	Severe: Fatigue that prevents normal activity
Gastrointestinal symptoms (nausea, vomiting, diarrhoea and/or abdominal pain)	0	Normal
	1	Mild: Gastrointestinal symptoms that are easily tolerated
	2	Moderate: Gastrointestinal symptoms that interfere with normal activity
	3	Severe: Gastrointestinal symptoms that prevent normal activity
Myalgia	0	Normal
	1	Mild: Myalgia that is easily tolerated
	2	Moderate: Myalgia that interferes with normal activity
	3	Severe: Myalgia that prevents normal activity
Shivering	0	None
	1	Shivering that is easily tolerated
	2	Shivering that interferes with normal activity
	3	Shivering that prevents normal activity

* The preferred route for recording temperature in this study is oral. When there is no other alternative, the temperature may be recorded by other route. If the temperature is taken by another route (axillary, rectal or tympanic), the route should be documented.

Note: Temperature will be recorded in the evening. Should additional temperature measurements be performed at other times of day, the highest temperature will be recorded in the eCRF and the time when the temperature was recorded.

The maximum intensity of local injection site redness/swelling will be scored at GSK Biologicals as follows using GSK Biologicals' standard grading scale based on the US Food and Drug Administration (FDA) guidelines for Toxicity Grading Scale for Healthy Adult and Adolescent Volunteers enrolled in Preventive Vaccine Clinical Trials [FDA, 2007]:

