## 7.1.2.1. Grading rules

The maximum intensity of local injection site redness/swelling will be scored at GSK Biologicals as follows using GSK Biologicals' standard grading scale based on the US Food and Drug Administration (FDA) guidelines for Toxicity Grading Scale for Healthy Adult and Adolescent Volunteers enrolled in Preventive Vaccine Clinical Trials [FDA, 2007]:

0	:	< 20 mm diameter
1	:	≥ 20 mm to ≤ 50 mm diameter
2	:	> 50 mm to ≤ 100 mm diameter
3	:	> 100 mm diameter

The investigator will assess the maximum intensity that occurred over the duration of the event for all unsolicited AEs (including SAEs) recorded during the study. The assessment will be based on the investigator's clinical judgement.

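### SAP Table 1's reactogenicity-grade rows omit subjects whose only solicited symptom is redness or swelling under 20 mm, and its Grade 3 row is not the ADL-preventing group named in the rationale

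*SAP*

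**What the plan says.** SAP Table 1 sets three rows under *Maximum Intensity / Reactogenicity Grade*:

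- Grade 0: "Subjects with no solicited symptoms reported".
- Grade 1,2: "Subjects with at least one grade 1 or 2 (=mild or moderate) solicited AE reported as maximum intensity".
- Grade 3: "Subjects with at least one grade 3 (=Severe) solicited AE reported as maximum intensity".

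No row is limited to particular symptoms. SAP 3.2 uses reactogenicity grade in the secondary objectives on the SF-36 PF scale, PF single items, Role Physical, QALY change, resource use and work loss. SAP 6.2.1 applies the Table 1 subgroups to the PF scale.

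The grading rules are of three kinds. Protocol Table 13 (section 8.3.3.2.1) grades pain, headache, fatigue, gastrointestinal symptoms, myalgia and shivering by tolerance and effect on activity. For redness and swelling the subject does only this: "Record greatest surface diameter in mm". SAP 7.1.2.1 then assigns grade 0 to "< 20 mm diameter" and grade 3 to "> 100 mm diameter"; the protocol has the same size rule. SAP 7.1.2.1 also grades temperature, with grade 3 above 39.0°C.

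Protocol 1.2.1 describes the grade in functional terms only: "Grade 3 reactogenicity is defined as preventing ADL". It makes that the study's question: "While grade 3 reactogenicity is defined as preventing ADL, there is no clear understanding available on how this translates to impact" on daily physical functioning.

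**The concern.** There are two separate problems.

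First, the Grade 0 definition rests on whether a symptom was reported, while the other two rows rest on intensity. Redness and swelling can be reported as present and still have intensity grade 0, so the rows may not cover everyone.

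Second, the Grade 3 row can include subjects whose grade says nothing about activity. If such subjects lose little PF or utility, they pull the row's mean loss towards zero. The row is expected to be small, so a few of them could matter. Protocol 1.2.1 says the data are meant for health care providers, policy makers and vaccinees, who may read the Grade 3 row as the effect of reactions that prevent daily activities.

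**Working it through.** **Which subjects have no row.** Apply the grading rules and then the written row definitions to subjects with one finding, and to one combined case.

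| Solicited findings | Maximum grade | Grade row | Type-of-symptom row |
|---|---|---|---|
| None | – | Grade 0 | None |
| Redness 10 mm or 19 mm only | 0 | no row | Local |
| Redness 20 mm only | 1 | Grade 1,2 | Local |
| Swelling 60 mm only | 2 | Grade 1,2 | Local |
| Redness 101 mm only | 3 | Grade 3 | Local |
| Temperature 39.1°C only | 3 | Grade 3 | General |
| Redness 10 mm plus mild headache | 1 | Grade 1,2 | Local and General |

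The no-row case arises because the eCRF screen in SAP Figure 4 records redness as Yes or No plus a size, with no 20 mm minimum. SAP 7.2.2.3 treats a Yes as presence of the symptom, separately from its intensity. Only redness and swelling can produce the gap. For the activity-graded symptoms, grade 0 means none or normal, and any temperature that meets the fever definition is at least grade 1. The combined case shows that one further symptom of grade 1 or more gives the subject a row.

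**What the Grade 3 row contains.** Six symptoms reach grade 3 by preventing activity. Redness and swelling reach it by diameter and fever by temperature. Table 1 pools all nine.

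**Possible size of the dilution.** Protocol 1.2.1 gives, from the pooled earlier trials, grade 3 pain of about 4% and grade 3 general symptoms of 3% or less per dose. Fever is a solicited general symptom, so that second figure also bounds it. No figure is given for grade 3 redness or swelling, nor for subjects who are Grade 3 on size or temperature alone. The following are therefore assumptions:

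- Activity-graded Grade 3: 16 subjects (0.04 × 400) to 40 subjects (10% of 400).
- Grade 3 on size or temperature only: 4 to 12 subjects (1% to 3% of 400).
- Change in the second group: zero.

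Reported loss as a fraction of the loss in activity-limited subjects = n_activity / (n_activity + n_size-or-temperature-only):

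- 40 / (40 + 4) = 0.91
- 16 / (16 + 12) = 0.57

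If the second group had half the loss instead of none:

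- (40 + 2) / 44 = 0.95
- (16 + 6) / 28 = 0.79

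**Against sampling error.** Borrow the planning SD of 21.2 from protocol 10.3 (an assumption for a subgroup). A row of 28 has a 95% half-width of 1.96 × 21.2 / √28 = 7.9 points. If the true loss in activity-limited subjects were 10 points (assumption), the 0.57 case would shift the row mean by 10 × (1 − 0.571) = 4.3 points.

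**Primary analysis.** The sample size reproduces: 1.96 × 21.2 / √360 = 2.19 against the stated 2.2, and 360 / 0.90 = 400. Neither it nor the overall primary estimate uses the grade rows.

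**The case against.** The pooled grade follows the protocol's operative rules. The ADL sentence is background prose placed directly after a figure for grade 3 pain. Protocol 8.3.3.2.1 itself grades redness and swelling in millimetres, and the secondary objectives ask for results by reactogenicity grade without limiting it to certain symptoms. This stands: Table 1 is a legitimate reading of the objective, and a reader who infers that the all-symptom grade is an error and must be replaced goes further than the documents do.

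Restricting the grade also has a cost. Activity-graded Grade 3 already means that normal activity was prevented, and PF asks whether health limits activities, so exposure and outcome come closer in content. This stands too, and is a reason to make the restricted grade a supplement.

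On Grade 0, the subgroup title and row label suggest maximum grade 0, so a programmer might derive it that way. But the written definition says otherwise, and nothing else in the SAP settles it. The table layouts are in separate annexes that are not available here and may contain a clarifying footnote.

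Finally, a reader might take 0.57 as the expected bias. It pairs the lowest activity-graded count, pain alone, with the highest assumed size- or temperature-only count. It also needs those 12 subjects to have no activity-graded Grade 3 symptom and no PF change. Subjects above 39.0°C or with swelling over 100 mm may well have milder activity-graded symptoms too. Even that case is a shift inside the row's confidence half-width.

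**Conclusion.** Both defects are present in the text, and both are limited.

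The Grade 0 definition leaves without a grade row any subject whose sole solicited finding is redness or swelling under 20 mm. It is tempting to say that all redness or swelling under 20 mm falls outside the rows. That is not so, because any other symptom of grade 1 or more gives the subject a row, and protocol 1.2.1 reports injection-site pain in up to 70% of recipients. How many subjects fall in the gap cannot be derived from the documents.

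The Grade 3 row mixes activity, size and temperature grades, so it does not by itself answer the rationale's question about reactions that prevent ADL. The dilution is unknown. The 0.57 to 0.91 range is illustrative and rests on assumed counts and zero PF change; with half the loss it is 0.79 to 0.95.

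The by-grade results are secondary, and protocol 10.7 sets no success criterion and calls the analyses descriptive. The primary estimate and the sample size do not change.

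**What to change.** In SAP Table 1:

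1. Define Grade 0 as no solicited symptom, or maximum solicited grade equal to 0. Subjects with only redness or swelling under 20 mm then have a row.
2. Keep the all-symptom grade as the planned presentation, and footnote that Grade 3 includes grades based on size and temperature.
3. Add a supplementary by-grade presentation of the PF, Role Physical, QALY, resource-use and work-loss results, using the highest grade among pain, headache, fatigue, gastrointestinal symptoms, myalgia and shivering only.

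The safety tables need no change. The cost is SAP wording, one more derived variable and one more set of tables, with no new data. The supplementary Grade 3 row will be somewhat smaller, and its exposure is closer in content to PF, which the table should say.

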5.5.2.2. Distribution, completion and collection of second pre-vaccination diary card

A second pre-vaccination diary card will be dispensed to each subject at Visit 2. The card will only query general symptoms and should be completed by the subject /subjects' caregiver(s) and collected by the site staff prior to the first study vaccination.

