8.1. Safety definitions

8.1.1. Definition of an adverse event

An AE is any untoward medical occurrence in a clinical investigation subject, temporally associated with the use of a medicinal product, whether or not considered related to the medicinal product.

An AE can therefore be any unfavourable and unintended sign (including an abnormal laboratory finding), symptom, or disease (new or exacerbated) temporally associated with the use of a medicinal product. For marketed medicinal products, this also includes failure to produce expected benefits (i.e., lack of efficacy), abuse or misuse.

Examples of an AE include:

- Exacerbation of a chronic or intermittent pre-existing condition including either an increase in frequency and/or intensity of the condition.
- New conditions detected or diagnosed after investigational vaccine(s)/product(s) administration even though they may have been present prior to the start of the study.
- Signs, symptoms, or the clinical sequelae of a suspected interaction.
- Signs, symptoms, or the clinical sequelae of a suspected overdose of either investigational vaccine(s)/product(s) or a concurrent medication (overdose per se should not be reported as an AE/SAE).
- Signs, symptoms temporally associated with vaccine administration.
- Pre- or post-treatment events that occur as a result of protocol-mandated procedures (i.e., invasive procedures, modification of subject's previous therapeutic regimen).

AEs to be recorded as endpoints (solicited AEs) are described in Section 8.1.3. All other AEs will be recorded as UNSOLICITED AEs.

Examples of an AE DO NOT include:

- Medical or surgical procedures (e.g., endoscopy, appendectomy); the condition that leads to the procedure is an AE/SAE.
- Situations where an untoward medical occurrence did not occur (e.g., social and/or convenience admission to a hospital, admission for routine examination).
- Anticipated day-to-day fluctuations of pre-existing disease(s) or condition(s) present or detected at the start of the study that do not worsen.
- Pre-existing conditions or signs and/or symptoms present in a subject prior to the first study vaccination. These events will be recorded in the medical history section of the eCRF.

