## 6.6. Analysis of safety

The primary analysis for safety will be based on the TVC. If the percentage of the vaccinated subjects excluded from the ATP cohort for safety is more than 5%, a second analysis based on the ATP cohort for safety will be performed.

Safety analyses will be performed by age stratum and frailty status (sub-groups are defined in [Table 1](#)).

When appropriate, tabulations will be presented overall and by time of occurrence relative to last vaccination (e.g., using windows such as Days 0 – 6, Days 0 – 29 and more than 30 days post-vaccination).

The following analyses will be performed for safety endpoints:

- The percentage of subjects with at least one local solicited AE, with at least one general solicited AE and with any solicited AE during the solicited 7-day follow-up period will be tabulated with exact 95% CI after each vaccine dose and overall. The same tabulation will be performed for grade 3; related and grade 3 related AEs;
- The percentage of subjects with at least one local AE (solicited and unsolicited), with at least one general adverse event (solicited and unsolicited) and with any AE during the solicited 7-day follow-up period will be tabulated with exact 95% CI after each vaccine dose and overall. The same tabulation will be performed for grade 3, related and grade 3 related AEs;
- The percentage of subjects reporting each individual general AE collected during the pre-vaccination period (Day -7 and Day 0 visits) will be tabulated with exact 95% CI.
- The percentage of subjects reporting each individual solicited local and general AE during the solicited 7-day-follow-up period will be tabulated with exact 95% CI. For all solicited symptoms, the same tabulation will be performed for grade 3 solicited AEs and for solicited general AEs with relationship to vaccination;
- Summary of temperature value by half degree increment reported during the 7-day (Days 0-6) post-vaccination period following each dose and overall doses and subjects. The same tabulation for fever with relationship to vaccination will be done;

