**ZOSTER-063 (204928): SOLICITED SYMPTOMS (Solicited symptoms)**

**SOLICITED ADVERSE EVENTS - GENERAL SIGNS/SYMPOTMS - TEMPERATURES - REACTOGENICITY TRIGGERED MEDICAL ATTENTION**

2.\* Has the subject experienced any of the General Solicited signs/symptoms between Day 0 and Day 6?

**1**

[GENSOL\_YN]  
[A:Y]  Yes -> Please:  
  
• tick No/Yes for each sign/symptom and complete further as necessary in the "General signs/symptoms (except temperature)" form,  
• complete "Temperatures" and "Reactogenicity triggered medical attention" forms.  
[A:N]  No -> Please complete the "Temperatures" form  
[A:U]  Unknown, no information available

Key: [\*] = Item is required  
Note: Hidden items are not displayed.  
Note: Source verification critical settings made in InForm will override any settings made in Central Designer.

**ZOSTER-063 (204928): SOLICITED ADVERSE EVENTS - GENERAL SIGNS/SYMPOTMS (EXCEPT TEMPERATURE) (General signs/symptoms (except temperature))**

If any of these adverse events meets the definition of serious, complete an Expedited Adverse Event Report.

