# Statistical Analysis Plan

GlaxoSmithKline

Study alias & e-track number(s): ZOSTER-063 (204928)

For each solicited general symptom if the answer to (2) in [Figure 2](#) is "No", the subject will be considered as not having that symptom after that dose.

**Subjects who documented the presence of a specific symptom** i.e., if the answer to (2) in [Figure 2](#) is "Yes" (ex FA\_YN=Y), the maximum intensity recording over the considered follow-up period is used for the analysis of the percentage of subjects with symptoms.

**If the subject answered "Yes" to (2) in [Figure 2](#) for a specific symptom BUT partially recorded daily measurement** (e.g. intensity missing for Day 3) over the considered solicited period, s/he will be included in the summaries and classified according to their maximum observed daily recording over the solicited period.

**If the subject answered "Yes" to (2) in [Figure 2](#) for a specific symptom BUT no daily measurement is recorded**, s/he will not be included and counted in the summary of subjects with symptoms above a specified threshold, however s/he will be part of the summary corresponding to the 'All' category.

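### SAP Table 1 counts general symptoms already present before vaccination as reactions, so the PF loss in the General row is expected to be pulled toward zero by an unknown amount

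*SAP*

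**What the plan says.** **How the rows are built.** SAP Table 1 puts a subject in General as one of the "Subjects with at least one solicited general symptom reported". Grade 0 and None hold subjects with no solicited symptom; the Grade 0 text is "Subjects with no solicited symptoms reported". Grade 1,2 and Grade 3 go by maximum intensity. Subjects can be in both General and Local.

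**What feeds them.** The eCRF entry question in SAP Figure 2 is "Has the subject experienced any of the General Solicited signs/symptoms between Day 0 and Day 6". It asks about presence, not whether the symptom is new or worse. For a symptom marked present, SAP 7.2.2.1 says "the maximum intensity recording over the considered follow-up period is used for the analysis of the percentage of subjects with symptoms". The same eCRF form records a causality answer for each general symptom. SAP 6.6 uses it in safety tables; Table 1 does not use it.

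**What is known before vaccination.** Every subject completes a general-symptom card at Visit 1 (Protocol 5.5.1.8) and another at Visit 2 before dose 1. Of the second, Protocol 5.5.2.2 says: "The card will only query general symptoms and should be completed by the subject". The only use stated in the SAP is a safety table in 6.6: "The percentage of subjects reporting each individual general AE collected during the pre-vaccination period (Day -7 and Day 0 visits) will be tabulated".

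**Related text.** Among things that are not adverse events, Protocol 8.1.1 lists "Pre-existing conditions or signs and/or symptoms present in a subject prior to the first study vaccination", along with expected day-to-day fluctuations that do not worsen. SAP 6.2.1 analyses PF in the Table 1 subgroups. SAP 6.2.1.2 takes the dose 1 baseline from Day -7 and Day 0.

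**The concern.** Consider a subject with moderate fatigue and myalgia on both pre-vaccination cards and on each day after the dose. Nothing changed at vaccination, and the complaint is already in the Day -7 and Day 0 PF scores. If the symptoms are entered as reported, Table 1 still files this subject under General. Such subjects add roughly zero change to a row meant to show what a general reaction costs.

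The case is foreseeable. About a third of enrolment is aged 70 or over, and the SAP's own frailty list includes arthritis and migraine, whose symptoms overlap with solicited myalgia and headache.

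Eight secondary objectives ask for results by reactogenicity grade and symptom type: PF scale, PF items, Role Physical, QALY, resource use, subject work loss and the two caregiver objectives. There is no placebo arm, so the pre-vaccination cards are the only diary data on background symptoms. Protocol 1.2.1 says the results will help vaccinators inform vaccinees; an understated loss among reactors bears directly on that.

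**Working it through.** **1. The plan's own figure.** Protocol 10.3 assumes an SD of 21.2 for PF change and states a precision of 2.2 with 360 subjects, inflated to 400 for 10% non-evaluable. Taking a two-sided 95% interval (the level is not stated there):

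- half-width = 1.96 × 21.2 / √360 = 2.19
- N for 2.2 = (1.96 × 21.2 / 2.2)² = 357, against 360
- 360 / 0.90 = 400

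The figure reproduces. It concerns the overall estimate, so it neither supports nor weakens this point.

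**2. General row: model.** Let v be the share of subjects with a vaccine-caused general symptom, b the share with a background one (independent of v), and g the share placed in General.

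- g = 1 − (1 − v)(1 − b), so 1 − v = (1 − g)/(1 − b)
- share of the row that is background only: s = b(1 − v)/g = b(1 − g)/[(1 − b)g]
- if background-only subjects have zero mean change, reported loss = (1 − s) × loss in true reactors

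**3. Inputs.** The documents give neither b nor g; both are assumed. Protocol 1.2.1 reports about 33% per dose for myalgia and fatigue. General covers six symptoms, so 33% is a low value for g. I take g = 33%, 50%, 65% and b = 5%, 10%, 20%.

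**4. Results (s, the relative understatement).**

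| g | b = 5% | b = 10% | b = 20% |
|---|---|---|---|
| 33% | 10.7% | 22.6% | 50.8% |
| 50% | 5.3% | 11.1% | 25.0% |
| 65% | 2.8% | 6.0% | 13.5% |

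Example: g = 50%, b = 10% gives 0.10 × 0.50 / (0.90 × 0.50) = 0.111. The 50.8% corner requires v = 1 − 0.67/0.80 = 16%, well below the 33% reported for single symptoms, so it is an outer bound rather than a likely value.

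**5. Any solicited symptom (Grade 1,2 and Grade 3 pooled).** Let a be the share with a local or vaccine-caused symptom. Injection-site pain alone reaches up to 70% (Protocol 1.2.1), so I assume a = 70-80%. The background-only share is b(1 − a)/[a + b(1 − a)]:

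- a = 80%, b = 5%: 0.010/0.810 = 1.2%
- a = 70%, b = 20%: 0.060/0.760 = 7.9%

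**6. Proportion.** With 360 evaluable and g = 50%, the row has 180 subjects and a half-width of 1.96 × 21.2/√180 = 3.10 points, using the overall SD. At s = 11.1% the shift would exceed that only if the true loss were above 3.10/0.111 = 28 points. At the 50.8% corner (119 subjects, half-width 3.81) the threshold is 3.81/0.508 = 7.5 points.

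**The case against.** **Protocol 8.1.1 may already exclude these symptoms.** If sites apply it to diary entries, unchanged complaints go to medical history and never reach Table 1, whose grade rows refer to solicited AEs. Staff review the cards with the subject before transcription. This is a fair point, but neither document says that 8.1.1 governs solicited entries, and the eCRF question asks only about presence. It supports asking for a statement; it does not close the gap.

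**Selection limits background symptoms.** An exclusion criterion removes significant illness whose medication might confound AE evaluation, and Protocol 6.4 allows vaccination to be postponed for acute disease or fever. Both reduce b. Neither removes ordinary chronic fatigue, headache or muscle pain.

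**Dilution is not demonstrated.** This stands. The background rate is unknown and zero change is an assumption. A real worsening in someone with a chronic complaint belongs in the row.

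**Most rows barely move.** This also stands. Local pain already places most subjects in a reacting grade, and Local is not defined by general symptoms.

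**A simple new-symptom flag can do harm.** If the cards carry no grade, a passing mild headache at Day -7 would remove a true severe reaction. There is also no card before dose 2, which comes 49-83 days after dose 1. Both points shape the fix.

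**Existing analyses.** The SAP 6.2.3 exclusion of unrelated events covers the primary endpoint only, so it does not address the subgroup rows.

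**Conclusion.** The point holds for the General row, and only slightly for Grade 0 and Grade 1,2. The definition ignores pre-vaccination information that the trial collects, and the expected direction is toward zero because baseline is measured at the same two visits as the cards. The size cannot be fixed from the documents: about 3-51% of the true General-row loss under b = 5-20%, g = 33-65%, independence and zero change in background-only subjects (11% in the middle of the grid), and about 1-8% for any solicited symptom.

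A reader might infer more. The documents do not support saying that the loss is in fact diluted, that all reactogenicity rows suffer alike, or that the primary result is biased:

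- The overall PF change includes every subject whatever the row, so it is unaffected.
- Local is unaffected, and Grade 3 is touched only by a background complaint that is itself grade 3.
- For QALY, the SAP model has no grade or symptom-type term, and the medication and medical-visit tables in SAP 6.4 are by age and dose. There the point rests on the objectives rather than on a specified table.

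Protocol 10.7 calls the analyses descriptive, with no success criterion. This is a cheap improvement to secondary results.

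**What to change.** Keep the Table 1 rows. In SAP 6.2.3, with a cross-reference in Table 1, add a sensitivity version beside the by-type and by-grade PF results, and beside Role Physical and QALY where those are produced by type or grade:

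- **Dose 1:** count a solicited general symptom only if it is absent from the Day -7 and Day 0 cards, or of higher grade than on them. If the cards carry no grade, also count an already-reported symptom when it is judged related to vaccination.
- **Dose 2:** there is no pre-dose card, so count general symptoms judged related.
- **Both doses:** keep all local symptoms and report how many subjects change row.
- State whether Protocol 8.1.1 governs solicited diary entries.

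Cost: one derived variable and one extra set of tables, with no new data. Limits: two pre-vaccination days catch intermittent symptoms only in part, causality is an open-label judgement, and some rows become slightly smaller. The sensitivity version should therefore stand beside the present rows, not replace them.
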